### 1.3 Grading of Acute GVHD

Acute GVHD is a heterogeneous set of disease processes that potentially involves multiple organ systems, with varying degrees of severity by organ system. Disease onset typically manifests most commonly in the skin, with the GI tract and liver as the next most common sites involved. Historically, classification systems of aGVHD have been established to segregate aGVHD according to severity. The severity grade of aGVHD has been shown to correspond to overall survival, with increased transplant-related mortality correlating with higher aGVHD grade.

One of the first grading systems, published by Glucksberg and colleagues in 1974, involves assigning a stage of 1 to 4 to each involved organ, as described in Table 2, and combining these stages to yield an overall grade ranging from I to IV (Table 3).

Another grading system, which was devised by the International Bone Marrow Transplant Registry (IBMTR) and used in Protocol MSB-GVHD001, classifies aGVHD severity on a scale of A to D. The selection of the IBMTR was based on the use of this scale in previous programs and studies with remestemcel-L, thereby allowing for use of historical controls from those studies. Table 3 presents a summary of the IBMTR grading systems for aGVHD based on stages of organ severity.

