## 9. STATISTICAL CONSIDERATIONS AND ANALYTICAL PLAN

### 9.1 Statistical Analysis Plan

Since this is an extension trial of MSB-GVHD001, data presented for MSB-GVHD002 will be presented in two ways:

1. For the extension period only. This will include assessments beyond Day 100.
2. For the entire period spanning both MSB-GVHD001 and MSB-GVHD002 trials.  
In particular, this includes time-to-event data (flares and therapy escalation), survival data, incidence of cGVHD, and frequency of flares.

Categorical variables will be summarized using frequencies and percentages. Continuous variables will be summarized using descriptive statistics (n, mean, standard deviation [SD], median, minimum, and maximum). Confidence intervals, if presented, will have a two-sided 95% confidence level. For time-to-event variables, Kaplan-Meier curves will be presented as appropriate.

In general, the baseline value for a variable is defined as the last non-missing observation prior to or equal to the first dose date of study treatment in MSB-GVHD001. Baseline for analyses of the entire period of MSB-GVHD001 and MSB-GVHD002 will be the same as baseline defined for Protocol MSB-GVHD001. The baseline for the extension period beyond Day 100 will be the same values at the end of study/Day 100 for MSB-GVHD001. Data collected at unscheduled time points will not be summarized at the unscheduled time points.

The actual day relative to start of treatment will be determined from the first dose date in Protocol MSB-GVHD001, which will be considered 'Study Day 0'. Study day will be calculated from the first infusion date in Protocol MSB-GVHD001. A detailed statistical analysis plan (SAP) will be finalized prior to the database lock.

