## **9.5 Secondary Endpoints Analysis**

### **9.5.1 Assessment of Survival at Day 180**

Survival will be assessed from initial remestemcel-L treatment to the end of study/Day 180. The numbers with percentages for survival, non-survival, or missing, including lost to follow-up, will be summarized at Day 180. For tabulating responders at Day 28 from the MSB-GVHD001 study versus survivors at Day 180 the present study, percentages of survivors and deaths will be based on all subjects, including those with missing survival information for the lost to follow-up or withdrawn subjects. The association between Day 28 OR and survival at Day 180, and between Day 28 VGPR and survival at Day 180, will be tested for statistical significance. First, the associations will be tested using a Cochran–Mantel–Haenszel (CMH) test, stratifying by baseline aGVHD grade. Day 180 survival Kaplan-Meier curves will be plotted by Day 28 responder and non-responder groups, and differences between these groups will be tested for any statistically significant difference using the log-rank test. The odds ratio for survival at Day 180, given responder status at Day 28, will be presented and tested for statistical significance (whether statistically significantly greater than 1).

[REDACTED]

[REDACTED]

[REDACTED]

[REDACTED]

[REDACTED]

[REDACTED]

[REDACTED]

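### Baseline aGVHD grade enters only the CMH test of Day 28 response against Day 180 survival; the log-rank test is unstratified as written and the odds-ratio estimator is not named

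*Combined protocol and SAP*

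**What the plan says.** Section 9.5.1 sets out three inferential analyses of one question.

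- **CMH test.** "The association between Day 28 OR and survival at Day 180, and between Day 28 VGPR and survival at Day 180" are each tested first by CMH, "stratifying by baseline aGVHD grade".
- **Log-rank test.** Kaplan-Meier curves are drawn by Day 28 responder status, and "differences between these groups will be tested for any statistically significant difference using the log-rank test". No stratification factor or covariate is given.
- **Odds ratio.** "The odds ratio for survival at Day 180, given responder status at Day 28, will be presented and tested for statistical significance", the question being "whether statistically significantly greater than 1". The text does not say whether this is a crude, Mantel-Haenszel or model-based odds ratio, and gives no alpha for the directional test.

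Three other places bear on this. Section 1.3 states that "The severity grade of aGVHD has been shown to correspond to overall survival", "with increased transplant-related mortality correlating with higher aGVHD grade". Section 9.3 lists baseline grade among the characteristics to be summarised, so the variable is available. Section 9.1 says "Confidence intervals, if presented, will have a two-sided 95% confidence level", and leaves further detail to a SAP due before database lock.

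**The concern.** Day 28 responders and non-responders are not randomised groups, so any baseline factor that predicts both response and survival will produce an association between the two. The protocol calls grade prognostic for survival and controls for it in the CMH test. The next two analyses of the same question then state no control for it.

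This matters because a CMH test yields a p-value. What a reader will remember is the pair of survival curves with its log-rank p-value, and the odds ratio. If those are unadjusted and milder cases respond more often, part or all of the apparent benefit of responding could simply be milder disease. The three results could also point different ways, with nothing in the plan to say which one prevails. An unnamed estimator leaves a choice open that could be made after the data are seen.

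**Working it through.** The plan gives no sample size, event count or effect size for this analysis, so there is no figure to reproduce. What follows is an illustration of how large the effect could be.

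**Inputs.** From the documents: grade is related to survival (Section 1.3) and only the CMH test is stratified (Section 9.5.1). Assumed, because the documents do not give them: grades B/C/D in proportions 20/40/40%, response and survival rates by grade, total N, exponential survival, no loss to follow-up, and the alpha levels of the directional tests. Within each grade, response and survival are independent, so the true within-grade odds ratio is 1.

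**Formula.** With grade share m, response rate r and survival rate s, the crude cells are a = Σ m·r·s, b = Σ m·r·(1−s), c = Σ m·(1−r)·s, d = Σ m·(1−r)·(1−s), and the crude odds ratio is ad/(bc).

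**Worked case.** Response 85/70/50%, survival 90/70/50%:

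- a = 0.153 + 0.196 + 0.100 = 0.449
- b = 0.017 + 0.084 + 0.100 = 0.201
- c = 0.027 + 0.084 + 0.100 = 0.211
- d = 0.003 + 0.036 + 0.100 = 0.139
- crude odds ratio = (0.449 × 0.139)/(0.201 × 0.211) = 0.06241/0.04241 = 1.47

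In 20,000 simulations per setting, a crude test at one-sided 2.5% rejected in 7 to 8% (N=40), 9% (N=55) and 12% (N=80) of trials; the stratified CMH test stayed at 2.4 to 2.8%. The crude test was significant while CMH was not in 5 to 9% of trials. Two milder settings gave crude odds ratios of 1.26 (response 85/75/60%, survival 85/70/55%) and 1.12 (80/70/60% for both).

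**Log-rank test and a wider range of settings.** Simulated rejection rates in %, given as N=50 / N=100 (2,000 and 1,000 runs):

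| Response B/C/D | Survival B/C/D | Crude odds ratio | Log-rank, unstratified (two-sided 5%) | Log-rank, stratified (two-sided 5%) | Crude directional test (one-sided 5%) | CMH directional test (one-sided 5%) |
|---|---|---|---|---|---|---|
| 70/70/70 | 85/70/50 | 1.00 | 4.8 / 4.2 | 5.3 / 4.1 | 4.9 / 5.1 | 4.9 / 5.8 |
| 75/70/60 | 80/70/60 | 1.10 | 5.5 / 6.9 | 4.6 / 5.8 | 7.2 / 8.7 | 5.2 / 5.9 |
| 80/70/55 | 85/70/50 | 1.29 | 7.6 / 8.9 | 5.0 / 5.5 | 10.8 / 12.9 | 4.4 / 5.2 |
| 90/70/40 | 95/70/35 | 2.22 | 27.7 / 49.3 | 6.0 / 6.2 | 38.5 / 61.0 | 5.6 / 5.7 |

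The simulation error near 5% is √(0.05 × 0.95/2000) = 0.5 points at N=50 and √(0.05 × 0.95/1000) = 0.7 points at N=100, so the stratified tests are close to nominal throughout. The first row is the important control: grade predicts survival strongly, but because response is the same in every grade there is no bias.

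**The case against.** A reader might infer that the plan reports an unadjusted odds ratio. The text does not say so. It names no estimator, and directly after a grade-stratified CMH test the Mantel-Haenszel common odds ratio would be a natural companion. If that is what is meant, the difficulty with the odds ratio largely disappears. What stands is that the estimator is undefined.

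A reader might also infer that the log-rank test and odds ratio are confounded. That needs grade to predict both survival and Day 28 response. Section 1.3 supports only the first link; the documents give no figure for the second, and the first row of the table shows no bias without it. Every magnitude above rests on assumed rates and sizes, and the largest come from steep gradients in both response and survival.

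The remaining objections lower the importance of the point without removing it. A detailed SAP is still to come and text after Section 9.5.1 is blacked out, so adjustment may be specified there; but Section 9.5.1 itself is readable and assigns strata to one test only. The adjusted CMH test comes first, so a grade-adjusted inference is already planned. The analysis is secondary and prognostic, not a treatment comparison. Finally, stratifying by grade does not address a separate matter: survival is counted from first infusion while the groups are defined at Day 28. That is true, and it needs its own remedy.

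**Conclusion.** The inconsistency is on the page: one of three analyses of the same association is adjusted for a factor the protocol calls prognostic, the log-rank test is not, and the odds ratio is undefined. Whether this produces bias depends on how strongly baseline grade predicts Day 28 response, which the documents do not report. With no within-grade association and a B/C/D mix of 20/40/40%, the crude odds ratio runs from 1.00 (equal response) through about 1.1 to 1.5 (mild to moderate gradients) to 2.22 (steep gradients). The matching false-positive rate of the unstratified log-rank test runs from nominal to 49.3%. The documents therefore support saying that these results may be confounded by severity and may disagree with the CMH test, and no more than that. The change is worth making because it is cheap and removes the question; the primary safety objective does not depend on it.

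**What to change.** In the SAP, before database lock:

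1. Stratify the log-rank test by baseline aGVHD grade, using the same strata as the CMH test.
2. Name the odds ratio as the Mantel-Haenszel common odds ratio, or as a grade-adjusted exact or penalised logistic odds ratio, and report it with the two-sided 95% interval of Section 9.1. State the sidedness and alpha of its test.
3. Keep the crude odds ratio, the unstratified log-rank result and the unadjusted curves as descriptive only.

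The cost is SAP wording, since baseline grade is already collected, plus some loss of precision if strata are sparse. For example, with an assumed N of 50 and the third row of the table, Grade B would hold 0.20 × 50 = 10 children, of whom 0.20 × 10 = 2 would be non-responders, with 0.15 × 10 = 1.5 expected deaths. Such a stratum adds little information, and none if it has no deaths or no non-responders. The SAP should therefore say in advance how sparse grades will be handled. The mismatch between first infusion as time origin and Day 28 grouping should be dealt with separately.

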**Secondary Endpoints**

1. Survival at 180 days for subjects who received the initial therapy through 28 days as outlined in Protocol MSB-GVHD001
2. GVHD activity at time points evenly divided amongst the term, from Day 100 to Day 180 specifically at Days 120, 140, 160 and 180 relative to baseline assessment in MSB-GVHD001.
3. Steroid doses at Days 120, 140, 160 and 180, including proportion of subjects able to taper steroids by 50% by each time point. Guideline for steroid taper is located in [Appendix 6](#).
4. Time to addition of any second-line GVHD treatment agent
5. The number of days to GVHD flares
6. Evidence of chronic GVHD at any time from Day 0 to Day 180. Guidelines for chronic GVHD assessment is located in [Appendix 8](#).

[REDACTED]

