### **2.3 Rationale for Subject Population**

This study will explore duration of response and evaluate the safety of remestemcel-L in pediatric subjects with aGVHD that has failed to respond to first-line systemic steroid treatment who participated in MSB-GVHD001. The safety population will be comprised of any subject who received at least one infusion of remestemcel-L in MSB-GVHD001. Survival at Day 180 will be evaluated. Additionally, duration of response will be explored in subjects who completed initial therapy of remestemcel-L (first 8 doses) in MSB-GVHD001 and responded to therapy, in order to best assess the impact of a response to treatment of aGVHD.

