### 3.3 Secondary Objectives:

1. To assess survival at 180 days
2. To obtain an assessment for GVHD activity to investigational medicinal product (IMP) administered in MSB-GVHD001.
3. To assess proportion of subjects able to taper steroids by 50% at each time point from Day 100 to Day 180.
4. To assess the time to addition of any second-line GVHD treatment agent
5. To assess the number of days to a GVHD flare
6. To evaluate subjects for evidence of chronic GVHD.

■ [REDACTED]

■ [REDACTED]

■ [REDACTED]

■ [REDACTED]

■ [REDACTED]

■ [REDACTED]

■ [REDACTED]

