#### 4.1.2 Secondary Endpoints

1. Survival at 180 days for subjects who received the complete initial therapy through 28 days as outlined in Protocol MSB-GVHD001
2. GVHD activity at time points evenly divided amongst the term from Day 100 to Day 180, specifically at Days 120, 140, 160 and 180, relative to baseline assessment in MSB-GVHD001.
3. Steroid doses at Days 120, 140, 160 and 180, including proportion of subjects able to taper steroids by 50% by each time point. Guideline for steroid taper is located in [Appendix 6](#).
4. Time to addition of any second-line GVHD treatment agent
5. The number of days to GVHD flares
6. Evidence of chronic GVHD at any time from Day 0 to Day 180. Guidelines for chronic GVHD assessment are located in [Appendix 8](#).

[REDACTED]

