#### **9.4.2 Survival to Day 180**

The number of subjects alive, deceased, lost to follow-up, or withdrawn from Day 0 (Protocol MSB-GVHD001) to Day 180 (Protocol MSB-GVHD002) will be summarized in a Subject Disposition table. For subjects who died, the time to event will be calculated from date of transplant, date of aGVHD onset, and date of treatment initiation. All other subjects will be censored and survival time will be calculated from the date of transplant, date of aGVHD onset, or date of treatment initiation to the date of last contact.

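### Section 9.5.1 compares survival from first infusion by Day 28 response with no landmark or stated test population, so deaths before Day 28 can bias all three tests towards response

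*Combined protocol and SAP*

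**What the plan says.** Section 9.5.1 sets the time origin: "Survival will be assessed from initial remestemcel-L treatment to the end of study/Day 180". It then forms groups by a status known only 28 days later: "Day 180 survival Kaplan-Meier curves will be plotted by Day 28 responder and non-responder groups". The curves are compared by log-rank. The association of Day 28 OR and of Day 28 VGPR with Day 180 survival is tested by CMH stratified by baseline grade, and an odds ratio is tested for being greater than 1. The visible text mentions no landmark, left truncation or time-dependent handling of response.

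The only population wording in the section concerns the responder-by-survivor table: "percentages of survivors and deaths will be based on all subjects, including those with missing survival information". That is a denominator rule for one table, not a population for the tests.

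Elsewhere the protocol points both ways.

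- **Restricted:** secondary endpoint 1 in the Synopsis is "Survival at 180 days for subjects who received the initial therapy through 28 days", and in Section 4.1.2 it is "Survival at 180 days for subjects who received the complete initial therapy through 28 days".
- **Unrestricted:** the matching objective in Section 3.3 is only "To assess survival at 180 days". Section 2.3 describes the safety population as "any subject who received at least one infusion of remestemcel-L in MSB-GVHD001. Survival at Day 180 will be evaluated". Section 9.1 presents survival data over both trials. Section 9.4.2 counts deaths "from Day 0 (Protocol MSB-GVHD001) to Day 180 (Protocol MSB-GVHD002) will be summarized in a Subject Disposition table".

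Table 4 defines a non-responder as anyone who does not achieve OR. It makes no exception for subjects who die before the assessment.

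**The concern.** This is immortal-time bias. Membership of the responder group guarantees survival to Day 28, while the non-responder group can absorb every earlier death. With the clock running from first infusion, those deaths count against non-response even if response has no bearing on what happens afterwards. The direction is fixed: it favours response.

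The tests are there to show whether Day 28 OR and VGPR go with Day 180 survival. Sections 1.4 and 2.2 lean on Day 28 response as a marker of later mortality, so a significant result here would be read as support for that in children given this product. If the result can arise from early deaths alone, it cannot carry that weight. Two programmers could also honestly implement the section on different sets and get different answers.

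**Working it through.** The plan states no sample size, response rate, Day 28 mortality or test level, so there is no figure of its own to reproduce. The calculation asks how large the bias would be if all treated children were analysed.

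**Inputs from the documents.** Time origin and grouping (Section 9.5.1); non-responder definition (Table 4); one-year survival of 5% to 30% in patients who do not respond to steroids (Section 1.2).

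**Assumptions.** Constant hazard; N = 55 (also 30 and 100); response among children alive at Day 28 of 30%, 50% or 70%; no link between response and survival after Day 28; all deaths by Day 28 included as non-responders. Tests count only rejections in favour of response, at cut-off 1.96 for log-rank and CMH (nominal 2.5%) and 1.645 for the odds ratio (nominal 5%). CMH uses three random strata; 0.5 is added to each cell for the odds-ratio test. There were 6,000 simulated trials per setting.

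**Step 1: survival at one-year survival 0.30.**
- S(28) = 0.30^(28/365) = 0.912, so 8.8% die by Day 28: 0.088 × 55 = 4.85 children.
- S(180) = 0.30^(180/365) = 0.552.
- From Day 28 to Day 180, s = 0.552 / 0.912 = 0.606.

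**Step 2: expected odds ratio.** Let e be the proportion dying by Day 28 and NR the proportion alive at Day 28 without response. Responder odds of survival are s/(1−s). Non-responder odds are NR·s / [NR(1−s) + e]. Hence OR = 1 + e / [NR(1−s)].
- 30% response: NR = 0.638, OR = 1 + 0.088/(0.638 × 0.394) = 1.35
- 50% response: NR = 0.456, OR = 1 + 0.088/(0.456 × 0.394) = 1.49
- 70% response: NR = 0.274, OR = 1 + 0.088/(0.274 × 0.394) = 1.82

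The true value is 1.0 throughout.

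**Step 3: false positives in favour of response, one-year survival 0.30.**

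| Setting | Test | 30% response | 50% | 70% |
|---|---|---|---|---|
| N = 55, all treated | log-rank | 6.6% | 13.9% | 31.5% |
| N = 55, all treated | CMH | 6.7% | 9.7% | 18.2% |
| N = 55, all treated | odds ratio > 1 | 9.6% | 16.9% | 27.4% |
| N = 30, all treated | log-rank | 4.1% | 9.2% | 20.5% |
| N = 100, all treated | log-rank | 9.9% | 24.2% | 47.9% |
| N = 55, Day 28 landmark | log-rank | 1.8% | 2.2% | 3.5% |
| N = 55, Day 28 landmark | CMH | 2.1% | 2.2% | 2.8% |
| N = 55, Day 28 landmark | odds ratio > 1 | 3.6% | 4.3% | 5.1% |

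**Step 4: sensitivity, N = 55.**
- One-year survival 50%: log-rank 4.8% to 19.9% over 30% to 70% response. One-year survival 5%: 13.2% to 63.2%.
- Share of early deaths included (separate simulation at one-year survival 30%; 30%/50%/70% response): all, 7%/16%/32%; half, 4%/7%/14%; none, 2% to 3%.
- Odds-ratio test at cut-off 1.96: 10% to 17% at 50% to 70% response, against a nominal 2.5%.

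**Step 5: a second calculation on different assumptions.** N = 40 or 60, response 50% or 70%, s = 0.70, two-sided 5% log-rank, 4,000 trials per setting.

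| Deaths before Day 28 | Expected OR | Log-rank rejections |
|---|---|---|
| 5% | 1.35 to 1.58 | 7% to 19% |
| 10% | 1.74 to 2.23 | 15% to 46% |
| 20% | 2.67 to 3.78 | 39% to 86% |

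With a Day 28 landmark the expected odds ratio is 1.0 and rejections are 4.3% to 5.5%.

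**The case against.** The strongest reply is that Section 9.5.1 analyses secondary endpoint 1, which is already limited to children treated through 28 days, so an analysis section need not repeat it. If that set is used, nearly everyone has reached about Day 28 and most of the bias goes. This stands as a reading, but Section 9.5.1 never invokes it. The restriction is also on treatment received, not on being alive and in follow-up at Day 28, and the clock would still start at first infusion.

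Section 9.2 requires entry into MSB-GVHD002, which could exclude early deaths. It does not do so reliably: Table 6, note a, lets consent be given together with the MSB-GVHD001 consent. Partial inclusion is therefore possible, and it shrinks the bias, as the half-included case shows.

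Other points stand in part:

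- Sections 2.3 and 9.4.2 can be read as serving the safety endpoint, Section 9.1 as setting a reporting period, and endpoint 1 as the more specific form of the Section 3.3 objective. They weaken the restricted reading but do not refute it.
- Table 4 does not mention children who died unassessed, and it defines responders for OR and CR but not for VGPR. Counting early deaths as non-responders follows its literal wording; it is not a stated rule.
- Text after Section 9.5.1 is redacted, and Sections 9.1 and 9.9 defer detail to the SAP. A landmark may be specified there.
- This is a secondary analysis in a study whose primary objective is descriptive safety.

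**Conclusion.** The concern holds, limited to the visible text and conditional on deaths before Day 28 entering the comparison. In that case the CMH, log-rank and odds-ratio tests are all biased towards response. In the main illustration (N = 55, one-year survival 30%), at 50% to 70% response, the odds ratio is inflated to 1.5 to 1.8 and the log-rank error favouring response rises to about 14% to 31% against 2.5%. At 30% response the figures are 1.35 and about 7%. With no such deaths in the set, this bias is absent.

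The direction does not depend on the assumptions; the size does. Sample size, response rates, constant hazard, test levels and the share of early deaths included are not in the documents, and the Section 1.2 survival range describes steroid non-responders in general. It should be fixed, because the better method is specific and cheap. Confidence is medium, given the redaction and the endpoint 1 wording.

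**What to change.** In Section 9.5.1 and the SAP, run the CMH, log-rank and odds-ratio analyses, for both OR and VGPR, as a Day 28 landmark:

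- include only children alive and in follow-up at Day 28;
- start the Kaplan-Meier and log-rank time at Day 28;
- state how this set relates to the endpoint 1 population in the Synopsis and Section 4.1.2, and to Section 9.2;
- report deaths before Day 28 separately.

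The cost is wording. Section 9.1 says the SAP is to be finalised before database lock, the Day 28 response and death dates are already needed for Sections 9.4.2 and 9.5.1, and no visits are added. The price is that a few early deaths leave the comparison, the result applies only to children alive at Day 28, and the association may look weaker.
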